19.3. Amendments and Study Termination

Changes to the research covered by this protocol must be implemented by formal protocol amendment. All amendments to the protocol must be initiated by the Sponsor and signed and dated by the Investigator. Protocol amendments must not be implemented without prior IRB or IEC approval. Documentation of amendment approval by the Investigator and IRB or IEC must be provided to the Sponsor or its authorized representative. When the change(s) involve only logistic or administrative aspects of the study, the IRB or IEC only needs to be notified.

During the course of the study, in situations where a departure from the protocol is unavoidable, the Investigator will contact the Medical Monitor. Except in emergency situations, this contact should be made before implementing any departure from the protocol. In all cases, contact with the Medical Monitor must be made as soon as possible to discuss the situation and agree on an appropriate course of action. The data recorded on the eCRF and source documents will reflect

any departure from the protocol and the source documents will describe the departure and the circumstances requiring it.

19.4. Financial Disclosure

Prior to the start of the study, Investigators will release sufficient and accurate financial information that permits the Sponsor to demonstrate that an Investigator and all study relevant assigned personnel have no personal or professional financial incentive regarding the future approval or disapproval of the study drug such that his or her research might be biased by such incentive.

20. PUBLICATION AND DISCLOSURE POLICY

It is understood by the Investigator that the information and data included in this protocol may be disclosed to and used by the Investigator's staff and associates as may be necessary to conduct this clinical study.

All information derived from this clinical study will be used by the Sponsor (or designee) and therefore, may be disclosed by the Sponsor (or designee) as required to other clinical Investigators, to the FDA, EMA, and to other government agencies, or in connection with intellectual property filings or publications. In order to allow for the use of the information derived from this clinical study, it is understood by the Investigator that there is an obligation to provide the Sponsor with complete test results and all data from this clinical study. The Investigator agrees to maintain this information in confidence, to use the information only to conduct the study, and to use the information for no other purpose without the Sponsor's prior written consent (or as otherwise may be permitted pursuant to a written agreement with the Sponsor or its designee).

The results of the study will be reported in a clinical study report prepared by the Sponsor (or designee), which will contain eCRF data from all clinical sites that conducted the study.

The Sponsor shall have the right to publish data from the study without approval from the Investigator. Manuscript(s) and abstract(s) may only be prepared through cooperation between the Sponsor (or designee) and the study Investigator(s). If an Investigator wishes to publish information from the study, a copy of the manuscript must be provided to the Sponsor for review in accordance with the provisions of such Investigator's written agreement with the Sponsor (or designee) before submission for publication or presentation. If requested by the Sponsor in writing, the Investigator will withhold such publication in accordance with the provisions of such agreement.

APPENDIX 1. SCHEDULE OF EVENTS

Visit	S1 ¹	T1	T2	T3	T4 ²
Week	-2	0	4	8	12/EOS
Procedure	Day -16 to -5	Day 1	Day 29 ± 5	Day 57 ± 5	Day 85 ± 5
Informed Consent	X				
Enrollment Criteria	X	X			
Demographics	X				
Medical History	X				
Concomitant\Prohibited Medications	X	X	X	X	X
Adverse Event Recording	X	X	X	X	X
Physical Exam		X			X
Weight ³	X	X ³	X	X	X
Height/BMI	X				
12-Lead ECG ⁴		X			X
Vital Signs ⁵	X	X	X	X	X
Serology ⁶	X				
Serum Pregnancy/FSH ⁷	X				
Urine Pregnancy		X			
TSH	X				
Clinical Safety Labs ⁸	X	X	X	X	X
Basic Fasting Lipids ⁹	X	X	X	X	X
Special Fasting Lipids and Other Biomarkers ¹⁰		X			X
HbA _{1C}	X				
Plasma Trough Study Drug			X	X	X
Randomization		X			
Double Blind Drug Dispensing		X	X	X	
Drug Return			X	X	X

BMI = body mass index; ECG = electrocardiogram; FSH = follicle-stimulating hormone, HbA_{1C} = hemoglobin A_{1C}; TSH = thyroid-stimulating hormone.

NOTE: For patients who withdraw from IMP treatment, they will continue to have visits according to the protocol schedule. Safety assessments should include clinical safety and basic lipid laboratories (except for apoB and hs-CRP), adverse events, PE, vital signs, and ECGs. For patients who withdraw from IMP treatment, but refuse to come to the clinic for assessments, assessments will take place by phone. The telephone contacts will occur according the protocol schedule with information regarding current health status and to collect information on AEs (e.g., recent procedures, hospitalizations, and if the patient has died, the cause of death).

¹ An optional visit approximately 10 days later MAY be completed if patient fails to meet specified entry criteria. If this optional visit is completed, the repeat value will be used to determine eligibility.

² All procedures will be completed at end of study or early termination.

³ Body weight will be measured in the morning while fasting, using consistent scales, after voiding, and without shoes and outerwear (e.g., coats).

⁴ Single 12-lead ECG will be collected prior to any blood sample collection.

⁵ Vital signs will include SBP, DBP, and HR, and will be collected prior to any blood sample collection. Patient will rest for 5 minutes prior to assessments.

⁶ Serology for Hep B antigen, Hep C antibody.

⁷ FSH completed in appropriate postmenopausal women only; pregnancy test completed in non-postmenopausal women only.

⁸ Clinical safety labs include hematology, blood chemistry, and urinalysis. Coagulation panel only if receiving anticoagulants that in the investigator's judgement requires monitoring (then test at T1 and repeat 3-5 days after starting IMP).

⁹ Basic fasting lipids include total cholesterol, calculated LDL-C, HDL-C, non-HDL-C, and triglycerides.

¹⁰Includes apoB and hs-CRP.

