6. INVESTIGATIONAL PLAN

6.1. Overall Study Design

This is a Phase 3, randomized, double-blind, parallel group, multicenter study of BA + EZE versus its individual components and placebo. Screening (S1) will occur approximately within 2 weeks prior to randomization. Patients who are deemed not eligible for randomization at any point during screening will be notified by clinical site personnel regarding their eligibility status and considered screen failures. Approximately 350 eligible patients will be randomized 2:2:2:1 on Day 1/Week 0 (T1) to receive either BA 180 mg + EZE 10 mg FDC (N = 100), BA 180 mg (n = 100), EZE 10 mg (n = 100), or placebo (n = 50) for 12 weeks. Randomized patients will return for clinic visits at Week 4 (T2), Week 8 (T3) and Week 12 (T4). Patients who withdraw from investigational medicinal product (IMP) treatment will be asked to continue to be followed for safety and efficacy using the protocol-specified visit schedule and procedures.

Eligible patients will have documented atherosclerotic cardiovascular diseases (ASCVD), heterozygous familial hypercholesterolemia (HeFH), and/or multiple cardiovascular risk factors and require additional LDL-C-lowering therapy despite receiving maximally tolerated statin background therapy. Maximally tolerated statin therapy may include statin regimens other than daily dosing or no statin at all (if not tolerated); however, doses of simvastatin \geq 40 mg/day are prohibited. A patient's currently used and maximally tolerated statin therapy will be determined by the investigator based on their medical judgment and local standard of care. Available sources, including the patient's self-reported history of lipid-modifying therapy will also be considered.

Patients will be stratified based on baseline/current statin intensity (high intensity statin versus other) and disease characteristics (ASCVD and/or HeFH versus multiple CV risk factors). High intensity statin includes atorvastatin 40-80 mg/day and rosuvastatin 20-40 mg/day, all others will be categorized as 'other' for randomization and stratification purposes. Definition of ASCVD and/or HeFH or multiple CV risk factors are provided in inclusion criteria. Enrollment will be monitored and a cap may be placed, if necessary, to ensure appropriate distribution into either of the statin intensity categories.

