10.5.4. Treatment Week 8 (Visit T3; Day 57 ± 5 days)

Patients will undergo the following assessments and procedures:

- Concomitant medication review (ongoing);
- Assess AEs and SAEs;
- Weight;
- Vital signs;
- Central clinical laboratory evaluations:
 - Hematology, blood chemistry, and urinalysis;
 - Basic fasting lipids (TC, calculated LDL-C, HDL-C, non-HDL-C, and TG);
- Trough PK sample;
- Return of IMP; assessment and recording of IMP dosing adherence;
- IWRS contact to obtain new MED ID number for double-blind IMP;
- Dispense double-blind IMP and provide dosing and storage instruction.

10.5.5. Treatment Week 12 (Visit T4; Day 85 ± 5 days)/End of Study or Early Termination

Patients will undergo the following assessments and procedures:

- Concomitant medication review (ongoing);
- Assess AEs and SAEs;
- PE;
- Weight;
- Vital signs;
- Central clinical laboratory evaluations:
 - Hematology, blood chemistry, and urinalysis;
 - Basic fasting lipids (TC, calculated LDL-C, HDL-C, non-HDL-C, and TG);
 - ApoB and hs-CRP;
- Trough PK sample;
- ECG;
- Return of IMP; assessment and recording of IMP adherence.

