10.6.3. Permanent Discontinuation of Investigational Medicinal Product

There may be situations where it may be necessary for a patient to permanently discontinue IMP.

Investigators should contact the Medical Monitor prior to permanent IMP discontinuation to discuss the situation. **If IMP is permanently discontinued, the patient will remain in the**

study to be evaluated for concomitant medications, efficacy and safety endpoints until the final study visit. If the patient is unwilling or unable to return for follow-up visits in person, alternatives such as telephone contact visits per the Schedule of Events, or telephone follow up at the end of the study should be used to collect as much data as possible. The follow-up frequency will be documented in the eCRF.

The reason for permanent discontinuation of IMP should be documented in the eCRF. If the discontinuation of IMP is due to an AE, the event should be documented in the eCRF. Some possible reasons that may lead to permanent early IMP discontinuation include:

- In the opinion of the investigator, any AE or a significant change in a laboratory value that warrants permanent discontinuation of IMP therapy. Investigators are advised to call the Medical Monitor prior to making such a decision;
- Illness, condition, or procedural complication (including AEs) affecting the patient's ability to participate or requiring prohibited medication. Investigators are advised to call the Medical Monitor prior to making such a decision;
- Female patients who become pregnant or are breastfeeding or who do not agree to use at least 1 reliable methods of birth control during the study (unless they have agreed to follow the definition of true abstinence) will be permanently discontinued from IMP;
- The patient requests to stop IMP permanently;
- The patient study blind is broken;
- Enrollment in any other clinical trial involving an investigational product or enrollment in any other type of medical research judged not to be scientifically or medically compatible with this study. If after discussion with the study Medical Monitor it is determined that the patient should not continue IMP, IMP will be discontinued;
- Patient moves away and it is impossible to come to this or any other trial site for visits as required by protocol.

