5.2 Statistical Analysis Plans

5.2.1 Analysis Population

5.2.1.1 Full Analysis Set (FAS)

The full analysis set (FAS), used for all of the efficacy analyses, is defined as all randomized patients. Patients in FAS will be analyzed in the treatment group they are randomized to regardless of the treatment received.

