Missing values for primary endpoint will be imputed using multiple imputation method, taking account for the adherence to the treatment. For patients with missing data and no longer receiving treatment at Week 12 (defined as lab date is > 7 days post last dose of IMP), their LDL-C will be imputed as their baseline value, for those with missing data but still receiving treatment, their LDL-C value will be imputed using a regression model based imputation model including treatment, stratification factor, baseline LDL-C as auxiliary variables. The imputation will be performed for 200 times and imputed datasets will be analyzed using an ANCOVA model with treatment, stratification as factors and baseline LDL-C as a covariate. Approximately 200 imputed datasets will be created; results from the analysis of each imputed dataset will be combined using Rubin's method. The final combined least squares mean (LSM) and standard error (SE) will be provided for both treatment groups, along with the LSM for each treatment comparison, its 95% confidence interval (CI) and associated p-value. More details will be provided in the programming specifications.

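### The schedule note excepts apoB and hs-CRP after withdrawal from study drug, against the efficacy follow-up text; separately, the valid Wilcoxon test for hs-CRP leaves baseline (as covariate) and strata unused

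*Protocol*

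**What the plan says.** **Sampling after withdrawal.** The note under Protocol Appendix 1 keeps withdrawn patients on the visit schedule and then limits their laboratories: "Safety assessments should include clinical safety and basic lipid laboratories (except for apoB and hs-CRP), adverse events, PE, vital signs, and ECGs". Other places point the other way:

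- Footnote 2 of the same schedule, attached to the Week 12 visit: "All procedures will be completed at end of study or early termination".
- Protocol 6.1, repeated in SAP 4.1, on patients who stop study drug: they "will be asked to continue to be followed for safety and efficacy using the protocol-specified visit schedule and procedures".
- Protocol 10.6.3: such a patient remains in the "study to be evaluated for concomitant medications, efficacy and safety endpoints until the final study visit".
- Protocol 10.5.5 (Week 12/End of Study or Early Termination) lists "ApoB and hs-CRP" without exception.

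Both markers are secondary endpoints and are scheduled only at Day 1 and Week 12. The SAP's copy of the schedule does not carry the note.

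**Analysis.** SAP 5.2.1.1: "The full analysis set (FAS), used for all of the efficacy analyses, is defined as all randomized patients". SAP 5.3.2 handles missing apoB as the primary endpoint is handled in 5.3.1. A missing value in a patient "no longer receiving treatment at Week 12 (defined as lab date is > 7 days post last dose of IMP") is set to baseline; otherwise it is imputed by regression. For hs-CRP, SAP 5.3.2 specifies a Wilcoxon rank-sum test with a Hodges-Lehmann estimate and interval, and gives skewness as the reason. It names no covariate or stratum, whereas the primary model in 5.3.1 uses both. The first SAP addendum titles the hs-CRP table as observed data on the FAS and the apoB table as multiple imputation on the FAS.

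**The concern.** Each marker has one post-baseline sample. If a site takes the note as an instruction not to sample, a withdrawn patient who attends Week 12 contributes LDL-C and non-HDL-C but neither apoB nor hs-CRP, and the value cannot be recovered later. An observed-data hs-CRP comparison then covers only patients still on drug under an all-randomised label. For apoB, an assumed value sits beside a measured non-HDL-C from the same visit. Sites that read the note differently would collect differently.

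The test is a separate and lesser matter. Skewness justifies working on ranks. It does not require setting aside baseline hs-CRP as a covariate or the randomisation strata, both of which are recorded for this trial.

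**Working it through.** **1. Which reading of the note fits the text.**

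- The sentence is framed as a list of safety assessments, so it could be describing only a safety set.
- Footnote 9 already defines basic fasting lipids without apoB or hs-CRP. The exception therefore adds nothing unless it tells sites not to draw them.
- The list includes physical examination and ECG, which after Day 1 are scheduled only at Week 12, the one post-baseline visit with apoB and hs-CRP.
- The list also includes basic lipids, which supply the efficacy endpoints, so it is not confined to safety measures.

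The restrictive reading is the more natural one. It conflicts with footnote 2 and with Protocol 6.1, 10.5.5 and 10.6.3.

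**2. hs-CRP: effect of omitting discontinuers.** The documents give no hs-CRP SD, correlation, effect or withdrawal rate. Assumed mid case: SD of log hs-CRP 1.0, baseline to Week 12 correlation 0.6, on-drug ratio of geometric means (GMR) 0.70. The effect is taken as fully lost off drug, and every discontinuer attends. With share p off drug in each arm, the all-randomised GMR is 0.70^(1−p). The other columns are simulated at 100 v 100, two-sided alpha 0.02. Differences are in percent change; on drug only, the Hodges-Lehmann difference is about −25.3.

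| Off drug | GMR, all | Hodges-Lehmann, all | Overstatement (points) | Wilcoxon power, on drug only | Wilcoxon power, all |
|---|---|---|---|---|---|
| 5% | 0.713 | −24.2 | 1.1 | 64% | 61% |
| 10% | 0.725 | −22.9 | 2.4 | 60% | 54% |
| 15% | 0.738 | −21.5 | 3.8 | 58% | 50% |
| 20% | 0.752 | −20.7 | 4.6 | 54% | 45% |

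Collecting the samples therefore lowers power. The reason to collect them is the quantity being estimated.

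**3. apoB: effect of setting to baseline.** Let s be the SD of percent change, Δ the on-drug effect and p the off-drug share, with off-drug mean 0. The arm variance is s² + p(1−p)Δ² if measured and (1−p)s² + p(1−p)Δ² if set to baseline. With s = 15, Δ = 20 and p = 0.10 (assumed):

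- measured: 225 + 36 = 261, SD 16.2;
- set to baseline: 202.5 + 36 = 238.5, SD 15.4, about 4% smaller.

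Over s 12 to 20, Δ 15 to 25 and p 5 to 15%, the reduction is 2 to 7%. If the true off-drug mean is −10%, an arm with 10% off drug shifts by 0.10 × 10 = 1 point.

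**4. hs-CRP: what adjustment gains.** Same mid case, no dropout. The alphas are those SAP 5.3.2 assigns to the step-down comparisons and apply only if hs-CRP is in it. The SD of log change is √(2(1−0.6)) = 0.894. After regression on baseline it is √(1−0.6²) = 0.8. With |ln 0.70| = 0.357, the approximate power is Φ(0.357/SD × √(3/π)/√(1/n₁+1/n₂) − z):

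- 100 v 100, alpha 0.02, z = 2.326: Wilcoxon Φ(2.755 − 2.326) = 67%; adjusted Φ(3.081 − 2.326) = 77%.
- 100 v 50, alpha 0.01, z = 2.576: Wilcoxon Φ(2.250 − 2.576) = 37%; adjusted Φ(2.515 − 2.576) = 48%.

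Simulation of the actual tests gives 66 v 76% and 36 v 45%. Across correlations 0.5 to 0.8 and GMR 0.70 to 0.75, rank ANCOVA gains 2.0 to 13.2 points at 100 v 100 and 5.0 to 10.1 at 100 v 50. Its simulated null rate is 0.0179 to 0.0213 at alpha 0.02 and 0.0084 to 0.0109 at 0.01.

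Nearly all of the gain comes from baseline. Strata change power by −0.2 to +0.1 points if they do not affect hs-CRP change. If each factor shifts log change by 0.2, they add 0.6 to 1.5 points (100 v 100) or 1.5 to 4.0 (100 v 50).

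**The case against.** The strongest reply on sampling is that the sentence concerns safety assessments, and that footnote 2 and Protocol 10.5.5 already tell sites to sample at Week 12. That reading is possible, and it is why the passages need reconciling rather than the sampling being called barred. It leaves the exception with no purpose, however.

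The size is also open to challenge. Appendix 1 and Protocol 10.6.3 move patients who will not attend to telephone contact, so no blood can be had from them, and a patient who stops shortly before Week 12 may retain some effect. Both points stand, so 1 to 5 points is an upper range.

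A reader might infer that apoB discontinuers drop out of the FAS. They do not: multiple imputation keeps them in, and if their true mean change is zero the baseline rule adds no bias to the mean.

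On the test, the Wilcoxon choice is prespecified, justified and valid, and percent change already uses baseline as its denominator. It also matches the Hodges-Lehmann interval, which rank ANCOVA does not: in the mid case at 100 v 100, 12.5% of simulated trials are significant by rank ANCOVA only and 2.3% by Wilcoxon only. Every power gain rests on assumed inputs. All of this stands and limits the point to efficiency.

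A reader might also infer that the SAP contradicts itself on how missing hs-CRP is handled. SAP 5.3.2 imputes the step-down endpoints and uses observed data for those outside Figure 2. That figure is not reproduced in the available text, and further imputation detail is deferred ("More details will be provided in the programming specifications"). No contradiction is shown.

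**Conclusion.** The conflict over sampling is real and should be reconciled. If the exception is followed, off-drug values of two secondary endpoints are lost. For hs-CRP on observed data, as the addendum table is titled, the FAS comparison becomes an on-drug one and overstates the all-randomised effect by at most about 1 to 5 percentage points at 5 to 20% off drug. That rests on the assumed mid case, with the effect fully lost and all discontinuers attending. For apoB the consequence is small. LDL-C is among the basic lipids that withdrawn patients keep, so the co-primary result is not affected.

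The Wilcoxon test is not an error. There is no bias or excess type I error to correct, only an efficiency gain of about 10 points of power in the mid case, mostly from baseline. The documents do not support calling the test wrong, or claiming a large benefit from strata: a shift of 0.4 in log change per factor, which larger strata gains need, exceeds the assumed drug effect of 0.357.

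**What to change.** (a) Reconcile the Appendix 1 note with footnote 2 and Protocol 6.1, 10.5.5 and 10.6.3. Delete the exception for apoB and hs-CRP, and add a sentence that patients withdrawn from study drug who attend Week 12 have all scheduled efficacy laboratories, including apoB and hs-CRP. Deletion alone is not enough, because footnote 9 leaves both markers out of the basic lipids that the note still names.

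Cost: a few more assays, a somewhat smaller observed effect and lower power (Wilcoxon about 60 to 54% with 10% off drug in the mid case). The documents do not show whether existing Week 12 tubes would suffice; that detail is left to the laboratory manual.

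(b) Keep the prespecified Wilcoxon test and Hodges-Lehmann interval. Add a labelled sensitivity analysis by rank ANCOVA: rank of percent change on treatment, rank of baseline hs-CRP and stratum. Before lock it could be the main test. The addenda show that unblinding has occurred, so for this trial only the sensitivity analysis remains.

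Cost: a few lines of code, and a p-value that may disagree with the Hodges-Lehmann interval, which the SAP should say.

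With (a) and (b) together, rank ANCOVA on all patients against Wilcoxon on drug only gives 71 v 64, 64 v 60, 59 v 58 and 53 v 54% power at 5, 10, 15 and 20% off drug (mid case, 100 v 100). Adjustment thus roughly pays for the fuller collection.

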APPENDIX 4. DUTCH LIPID CLINIC NETWORK CRITERIA FOR FAMILIAL HYPERCHOLESTEROLEMIA

Dutch Lipid Clinic Network Diagnostic Criteria for Familial Hypercholesterolemia^{1,2,3}

Diagnostic Scoring for Familial Hypercholesterolemia	
CRITERIA	POINTS POSSIBLE
Family History	
First-degree relative with known premature ^a coronary and vascular disease, OR First-degree relative with known LDL-C above the 95 th percentile	1
First-degree relative with tendinous xanthomata and/or arcus cornealis, OR Children aged less than 18 years with LDL-C level above the 95 th percentile	2
Clinical History	
Patient with premature ^a coronary artery disease	2
Patient with premature ^a cerebral or peripheral artery disease	1
Physical Examination	
Tendinous xanthomata	6
Arcus cornealis prior to age 45 years	4
Cholesterol Levels mg/dL (mmol/L)	
LDL-C \geq 330 mg/dL (\geq 8.5 mmol/L)	8
LDL-C 250-329 mg/dL (6.5-8.4 mmol/L)	5
LDL-C 190-249 mg/dL (5.0-6.4 mmol/L)	3
LDL-C 155-189 mg/dL (4.0-4.9 mmol/L)	1
DNA Analysis	
Functional mutation in the LDLR, apoB, or PCSK9 gene	8

apoB = apolipoprotein B; LDL-C = low-density lipoprotein cholesterol; LDLR = low-density lipoprotein receptor; FH = familial hypercholesterolemia; PCSK9 = Proprotein convertase subtilisin/kexin type 9.

^a Premature \leq 55 years in men; \leq 60 years in women

Scoring:

Diagnosis (Diagnosis Based Upon Total Score Obtained)	
Definite Familial Hypercholesterolemia	>8
Probable Familial Hypercholesterolemia	6-8
Possible Familial Hypercholesterolemia	3-5
Unlikely Familial Hypercholesterolemia	<3

References:

APPENDIX 5. SIMON BROOME REGISTER DIAGNOSTIC CRITERIA FOR HETEROZYGOUS FAMILIAL HYPERCHOLESTEROLEMIA

Simon Broome Diagnostic Criteria for Familial Hypercholesterolemia¹

Definite Familial Hypercholesterolemia:

- Required laboratory = high cholesterol levels:
 - Adult = Total cholesterol levels >290 mg/dL (7.5 mmol/L) or LDL-C >190 mg/dL (4.9 mmol/L)
 - Child less than 16 years of age = Total cholesterol levels >260 mg/dL (6.7 mmol/L) or LDL-C >155 mg/dL (4.0 mmol/L)
- Plus at least one of the two:
 - Plus physical finding = tend xanthomas, or tendon xanthomas in first or second degree relative

OR

- DNA-based evidence of an LDL-receptor mutation, familial defective apoB-100, or PCSK9 mutation

Possible Familial Hypercholesterolemia:

- Required laboratory = high cholesterol levels:
 - Adult = Total cholesterol levels >290 mg/dL (7.5 mmol/L) or LDL-C >190 mg/dL (4.9 mmol/L)
 - Child less than 16 years of age = Total cholesterol levels >260 mg/dL (6.7 mmol/L) or LDL-C >155 mg/dL (4.0 mmol/L)
- Plus at least one of the two:
 - Family history of myocardial infarction at:
 - Age 60 years or younger in first degree relative
 - Age 50 years or younger in second degree relative

OR

- Family history of elevated total cholesterol
 - Greater than 290 mg/dL (7.5 mmol/L) in adult first or second degree relative
 - Greater than 260 mg/dL (6.7 mmol/L) in child, brother or sister aged younger than 16 years

References:

**APPENDIX 6. ESTIMATED PERCENTILES OF CAC BY AGE
CATEGORY, GENDER, AND RACE/ETHNICITY**

Percentiles by Race	Women, n				Men, n			
	Age, y				Age, y			
	45–54	55–64	65–74	75–84	45–54	55–64	65–74	75–84
White, n	379	356	379	194	321	325	375	174
25th	0	0	0	20	0	0	21	103
50th	0	0	13	106	0	28	145	385
75th	0	16	119	370	22	155	540	1200
90th	8	102	391	921	110	452	1345	2933
95th	31	209	674	1535	207	743	2271	4619
Chinese, n	109	107	103	52	102	94	102	50
25th	0	0	0	0	0	0	0	11
50th	0	0	5	32	0	5	34	81
75th	0	18	70	146	14	67	174	305
90th	12	105	246	398	89	242	487	769
95th	44	213	436	656	184	429	803	1299
Black, n	274	241	278	110	214	192	206	98
25th	0	0	0	0	0	0	0	23
50th	0	0	0	47	0	0	32	141
75th	0	5	77	214	2	40	191	516
90th	9	74	310	582	45	173	575	1281
95th	38	173	561	953	105	318	945	2176
Hispanic, n	218	196	169	86	205	177	149	75
25th	0	0	0	0	0	0	1	36
50th	0	0	1	45	0	3	56	153
75th	0	2	51	205	9	75	247	494
90th	2	50	203	557	88	291	666	1221
95th	18	118	361	917	195	512	1091	1943

Reference:


APPENDIX 7. SUMMARY OF CHANGES IN AMENDMENT 1

SUMMARY OF CHANGES CLINICAL STUDY PROTOCOL

Study Number:	1002FDC-053
Study Title:	A Randomized, Double-Blind, Parallel Group Study to Evaluate the Efficacy and Safety of Bempedoic Acid 180 mg + Ezetimibe 10 mg Fixed-Dose Combination Compared to Bempedoic Acid, Ezetimibe, and Placebo Alone in Patients Treated with Maximally Tolerated Statin Therapy
Protocol Version Incorporating Current Summary of Changes:	Amendment 1: 18 October 2017
Preceding Protocol Version:	Original Protocol: 03 August 2017
Investigational Product Name:	ETC-1002

Conventions used in this Summary of Changes Document

1. The text immediately preceding and following a change to the protocol is included for each change in order to provide the reviewer with a reference point to identify the change in the protocol.
2. All locations (ie, section numbers and/or header text) refer to the current protocol version, which incorporates the items specified in this Summary of Changes document.
3. The original text is from the preceding protocol version.
4. In the “New Text”, all substantive text added to the protocol is italicized.
5. In the “New Text”, text deleted from the protocol is indicated in strikethrough font.

Summary and Justification of Changes

The protocol was amended for the following:

- Made administrative changes throughout protocol where required to correct inconsistencies, add clarification, or correct errors.
- Added instructions for collection, processing, and analysis of plasma trough bempedoic acid and ezetimibe concentrations. This new assessment was added to generate additional data describing these plasma trough IMP concentrations in a large clinical study.

- Added instruction to delay ingestion of IMP on clinic visit days until all study procedures have been completed. This instruction was added to enable accurate analysis of plasma trough IMP concentrations.
- Modified description of drug kit to indicate that 4, not 3, blister packs would be provided in each kit. Four blister packs are needed to supply sufficient drug for 4-week intervals between treatment visits.
- Modified instruction for acceptable contraception to functional, not started, on Day 1 to ensure adequate coverage while IMP is being administered.
- Added instruction to record prior use of statin at any point in the past, not just within 6 weeks prior to screening. Extended statin history will provide additional details regarding statins that may have been stopped in the past due to intolerable adverse effects.
- Added comment to exclusion criterion that if test for hepatitis C antibody is positive, but optional reflexive test for hepatitis C RNA is negative, patient can be enrolled.
- Removed erroneous statements that DMC and CEC would review data from this study on an ongoing basis.
- Added instruction to inclusion criteria that multiple risk factors of blood pressure, age and HDL-C should be assessed at Week -2 (Visit S1).
- Added clarification that ezetimibe is prohibited unless it is study supplied.
- Removed reference to randomization number since no specific number is generated.
- Added a definition for the PK analysis population.
- Added detail that an independent bio-analytical lab will be aware of treatment assignment during the treatment period only to support pharmacokinetic sample analysis.

CHANGE 1 REVISION OF TITLE PAGE VERSION INFORMATION

Location:

Title Page

Original Text:

Version	Date
Original Protocol:	03 August 2017

New Text:

Version	Date
Original Protocol:	03 August 2017
Amendment 1:	18 October 2017

CHANGE 2 REVISION TO EXPLORATORY OBJECTIVES

Location:

Section 2, Synopsis; Section 5.1.3, Exploratory Objective

Original Text:

- To assess the efficacy BA 180 mg + EZE 10 mg FDC versus placebo alone, BA alone, and EZE alone on percentage of patients attaining LDL-C <70 mg/dL after 12 weeks of treatment

New Text:

- To assess the efficacy BA 180 mg + EZE 10 mg FDC versus placebo alone, BA alone, and EZE alone on percentage of patients attaining LDL-C <70 mg/dL after 12 weeks of treatment;
- *To characterize the plasma trough concentrations of BA and/or EZE when administered as BA 180 mg + EZE 10 mg FDC, BA alone, and EZE alone.*

CHANGE 3 ADDITION OF CRITERIA FOR EVALUATION

Location:

Section 2, Synopsis

New Text:

Plasma Trough IMP

Plasma trough concentrations of BA (ETC-1002 and its active metabolite ESP15228) and EZE (glucuronidated EZE and unconjugated EZE)

CHANGE 4 REVISION TO STUDY ENDPOINTS

Location:

Section 2, Synopsis; Section 5.2.3, Exploratory Endpoints

Original Text:

Exploratory endpoints:

- Proportion of patients attaining LDL <70 mg/dL at Week 12 in BA 180 mg + EZE 10 mg FDC-treated arm compared to BA 180 mg arm, EZE 10 mg arm and placebo arm

New Text:

Exploratory endpoints:

- Proportion of patients attaining LDL <70 mg/dL at Week 12 in BA 180 mg + EZE 10 mg FDC-treated arm compared to BA 180 mg arm, EZE 10 mg arm and placebo arm;
- *Plasma trough concentrations at Weeks 4, 8, and 12 of BA (ETC-1002 and its active metabolite ESP15228) and EZE (glucuronidated EZE and unconjugated EZE) in BA 180 mg + EZE 10 mg FDC-treated arm, BA-treated arm, and/or EZE alone treated arm.*

CHANGE 5 REVISION TO INCLUSION CRITERIA

Location:

Section 2, Synopsis; Section 7.1, Patient Inclusion Criteria

Original Text:

3. Men and nonpregnant, nonlactating women,

Women must be either:

- Naturally postmenopausal reported by the patient and defined as:
 - ≥ 55 years and ≥ 1 year without menses, or
 - < 55 years and ≥ 1 year without menses with follicle-stimulating hormone (FSH) ≥ 40.0 IU/L,
- Surgically sterile including hysterectomy, bilateral oophorectomy, or tubal ligation or;
- Women of childbearing potential willing to use at least 1 acceptable method of birth control. The minimal requirement for adequate contraception should be started on Day 1, continuing during the study period and for at least 30 days after the last dose of study drug. Acceptable methods of birth control include:

6. Meeting the definition for at least 1 of the following 3 categories (ASCVD, HeFH, multiple cardiovascular risk factors):
 - c. Multiple cardiovascular risk factors defined as diabetes + 1 other risk factor or 3 risk factors that may include:
 - a. Age (men \geq 45 years; women \geq 55 years)
 - b. Family history (coronary heart disease in a first degree relative, men $<$ 45 years; women $<$ 55 years)
 - c. Smoking (current smoker)
 - d. Hypertension (Systolic blood pressure \geq 140 mmHg, diastolic blood pressure \geq 90 mmHg and/or on antihypertensive medications)
 - e. Low HDL-C ($<$ 40 mg/dL)
 - f. Coronary calcium score $>$ 95% for age/sex (see Appendix 6)

New Text:

3. Men and nonpregnant, nonlactating women,

Women must be either:

- Naturally postmenopausal reported by the patient and defined as:
 - \geq 55 years and \geq 1 year without menses, or
 - $<$ 55 years and \geq 1 year without menses with follicle-stimulating hormone (FSH) \geq 40.0 IU/L,
- Surgically sterile including hysterectomy, bilateral oophorectomy, or tubal ligation or;
- Women of childbearing potential willing to use at least 1 acceptable method of birth control. The minimal requirement for adequate contraception should be **started functional** on Day 1, continuing during the study period and for at least 30 days after the last dose of study drug. Acceptable methods of birth control include:

6. Meeting the definition for at least 1 of the following 3 categories (ASCVD, HeFH, multiple cardiovascular risk factors):
 - c. Multiple cardiovascular risk factors defined as diabetes + 1 other risk factor or 3 risk factors that may include:
 - a. Age (men \geq 45 years; women \geq 55 years) **at Week -2 (Visit S1);**
 - b. Family history (coronary heart disease in a first degree relative, men $<$ 45 years; women $<$ 55 years);
 - c. Smoking (current smoker);

- d. Hypertension (Systolic blood pressure ≥ 140 mmHg, diastolic blood pressure ≥ 90 mmHg and/or on antihypertensive medications) **at Week -2 (Visit S1);**
- e. Low HDL-C (<40 mg/dL) **at Week -2 (Visit S1);**
- f. Coronary calcium score $>95\%$ for age/sex (see Appendix 6)

CHANGE 6 REVISION TO EXCLUSION CRITERIA

Location:

Section 2, Synopsis; Section 7.2, Patient Exclusion Criteria

Original Text:

8. Liver disease or dysfunction, including:

- Alanine aminotransferase (ALT), aspartate aminotransferase (AST) $\geq 2 \times$ ULN, and/or total bilirubin (TB) $\geq 2 \times$ ULN at Week -2 (Visit S1). If TB $\geq 1.2 \times$ ULN, a reflex indirect (unconjugated) bilirubin will be obtained and if consistent with Gilbert's disease or if the patient has a history of Gilbert's Disease, the patient may be enrolled in the study.

Note: If a patient fails to meet ALT and/or AST criteria, an optional single repeat visit/measurement can, at the discretion of the investigator, be completed up to a maximum of 10 days later. For those patients who have a repeat ALT and/or AST measurement, the repeat value will be used to determine eligibility.

New Text:

8. Liver disease or dysfunction, including:

- Alanine aminotransferase (ALT), aspartate aminotransferase (AST) $\geq 2 \times$ ULN, and/or total bilirubin (TB) $\geq 2 \times$ ULN at Week -2 (Visit S1). If TB $\geq 1.2 \times$ ULN, a reflex indirect (unconjugated) bilirubin will be obtained and if consistent with Gilbert's disease or if the patient has a history of Gilbert's Disease, the patient may be enrolled in the study.

Note: If a patient fails to meet ALT and/or AST criteria, an optional single repeat visit/measurement can, at the discretion of the investigator, be completed up to a maximum of 10 days later. For those patients who have a repeat ALT and/or AST measurement, the repeat value will be used to determine eligibility. *Also, if test for hepatitis C antibody is positive, but optional reflexive test for hepatitis C ribonucleic acid (RNA) is negative, patient can be enrolled.*

CHANGE 7 REMOVAL OF CEC AND DMC REVIEW STATEMENTS

Location:

Section 2, Synopsis, Criteria for Evaluation; Section 13.2.1, Definition of Serious Adverse Event

Original Text:

Lipid and Cardiometabolic Assessments:

- Calculated LDL-C, HDL-C, non-HDL-C, TC, TG, and apoB
 - If TG exceeds 400 mg/dL (4.5 mmol/L) or LDL-C is \leq 50 mg/dL (1.3 mmol/L), direct measure of LDL-C will be conducted and will be used in the analyses
- hs-CRP

Safety Assessments:

Treatment-emergent adverse events (TEAEs), serious adverse events (SAEs), and adverse events of special interest (AESIs) will be reported by treatment group. Clinical endpoints will be collected and adjudicated by an independent Clinical Event Committee (CEC). Other safety assessments will include clinical safety laboratories (including hematology, blood chemistry, HbA_{1C}, and urinalysis), physical examination (PE) findings, vital signs, electrocardiogram (ECG) readings, and weight.

New Text:

Lipid and Cardiometabolic Assessments:

- Calculated LDL-C, HDL-C, non-HDL-C, TC, TG, and apoB
 - If TG exceeds 400 mg/dL (4.5 mmol/L) or LDL-C is \leq 50 mg/dL (1.3 mmol/L), direct measure of LDL-C will be conducted and will be used in the analyses
- hs-CRP

Safety Assessments:

Treatment-emergent adverse events (TEAEs), serious adverse events (SAEs), and adverse events of special interest (AESIs) will be reported by treatment group. ~~Clinical endpoints will be collected and adjudicated by an independent Clinical Event Committee (CEC).~~ Other safety assessments will include clinical safety laboratories (including hematology, blood chemistry, HbA_{1C}, and urinalysis), physical examination (PE) findings, vital signs, electrocardiogram (ECG) readings, and weight.

Original Text:

